7.2. Clinical Laboratory Data

All laboratory parameters will be normalized by converting values in original units to values in SI units and classified as normal, abnormal low, or abnormal high on normal ranges supplied by the local laboratories and upon employing standardization.

Observed and change from baseline of clinical laboratory data (hematology, serum chemistry, coagulation and continuous urinalysis parameters) will be summarized at each analysis visit by disease group.

Urinalysis categorical data will also be tabulated at each analysis visit by disease group, if applicable.

Shift table of normal, abnormal low and abnormal high from baseline by analysis visit will also be summarized for hematology and chemistry (including coagulation) data (scheduled or unscheduled) by disease. Denominator will be based on number of subjects who have non-missing baseline values.

All summary tables will be presented for Part B and Part A + B.

Clinical laboratory data will be listed by disease group. The listing will include changes from Part A + B and Part B baseline values and values that are outside the reference range will be flagged. Out of range laboratory results with their corresponding changes from baseline will also be listed.

In addition, liver abnormality will be summarized at each analysis visit including following variables by disease group:

- ALT or AST \geq 3×ULN
- ALT or AST \geq 3×ULN and (TBL >2×ULN or INR >1.5)
- ALT or AST \geq 5×ULN
- ALT or AST $>8 \times ULN$

Clinical laboratory test values are potentially clinically significant (PCS) if they meet either the low or high PCS criteria listed in Table 1 below:

	Criteria
Parameter	Lower limit
	Higher limit
Hematology	
WPC (total) $(x 10^{0}/1)$	< 3.0
wbc (total) (x10 9/L)	> 16
	< 0.5
Lymphocyte $(x10^{9}/L)$	< 0.8
	> 12
	< 1.0
Neutrophils (x10^9/L)	< 1.5
	> 12
DDC(-10.12/L)	< 3.3
$RBC(X10^{12}/L)$	> 6.8
Hemoglobin (g/dL)	< 10
Platalat count $(x10^{0}/I)$	< 100
	> 600
Serum Chemistry	
ALT	$> 1.5 \mathrm{xULN}$
	> 3.0xULN
AST	> 1.5xULN
	> 3.0xULN
ALP	> 1.5xULN
	> 3.0xULN
Total Serum Bilirubin	> 1.5xULN
GGT	> 3.0xULN
ALT or AST $>$ 3xULN and concurrent elevated total bilirubin defined as	> 2.0xULN

Table 1: Criteria for Potentially Clinically Significant Laboratory Tests

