### 13.5.1. Liver Toxicity

Drug treatment continuation will be evaluated in case of any signs of possible drug-induced hepatic injury as follows:

Drug treatment will be discontinued immediately if either:

• ALT or AST is  $>3 \times$  the upper limit of normal (ULN) and (total bilirubin is  $>2 \times$  ULN or international normalized ratio [INR] is >1.5)

or

• ALT or AST is >8× ULN

Drug treatment will be withheld if either:

• ALT or AST is >5× ULN

or

• ALT or AST is >3× ULN with the appearance of fatigue, nausea, vomiting, right upper quadrant pain or tenderness, fever, rash, and/or eosinophilia (>5%).

Drug treatment will be permanently discontinued and the subject withdrawn from the study if the condition persists for more than 2 weeks.

If the subject is not withdrawn from the study, drug treatment may be resumed when both ALT and AST are less than 1.5× ULN.

Any possible hepatic abnormalities will be monitored with repeat testing at a frequency of at least every 72 hours. Frequency of retesting will decrease to weekly or less once abnormalities stabilize. Repeat testing will discontinue once abnormalities are no longer detected.

Causes for the significant liver test abnormalities will be investigated (eg, acute viral hepatitis, Epstein-Barr virus, cytomegalovirus, herpes simplex virus, toxoplasmosis, varicella, and parvovirus) and subjects will be followed up until all abnormalities return to normal or to the baseline state.

Work-up will also include consideration of alcoholic and autoimmune hepatitis, hepatobiliary disorders (eg, gallstones), nonalcoholic steatohepatitis, cardiovascular causes (eg, right-sided heart failure), and concomitant medications or supplements.

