13.4. Definition of Visit Windows

Data will be summarized and analyzed based on the list of visits specified in the schedule of assessments of the protocol. All the records post-baseline will be assigned to an appropriate analysis visit using the following:

- For the post-baseline visits, the lower and the upper bound for the analysis visit windows are defined as the midpoints of the target date of the scheduled visits.
- If the date of assessment falls in between the lower bound and the upper bound for a visit as specified in the schedule of assessments of the protocol, then it will be assigned to that visit.
- If the interval separating 2 scheduled visits is an even number of days, the middle day will be included in the lower bound of the next visit.
- If more than 1 record is within the same analysis visit window, the record closest to the midpoint of the interval will be used in the analysis.
- If 2 records are tied before and after the middle of the interval, the earlier record will be used in the analysis.

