13.5. Repeated or Unscheduled Assessments of Safety Parameters

For safety parameters, if a subject has repeated assessments before the start of investigational product, then the results from the final assessment made prior to the start of investigational product will be used as baseline. If end of study assessments is repeated or unscheduled, the last post-baseline assessment will be used as the end of study assessment for generating descriptive statistics. However, all post-baseline assessments will be used for Potentially Clinically Significant (PCS) value determination and all assessments will be presented in the data listings.

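### The liver-abnormality table uses one record per visit window whatever its severity, so a transaminase peak found on a protocol retest can be missing from it, and the SAP specifies no any-time subject count

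*SAP*

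**What the plan says.** SAP 7.2 lists four liver criteria: ALT or AST ≥3x ULN; ≥3x ULN with total bilirubin >2x ULN or INR >1.5; ≥5x ULN; and >8x ULN. Its only instruction for them is that "liver abnormality will be summarized at each analysis visit including following variables by disease group".

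SAP 13.4 decides which results reach a by-visit table. First, "All the records post-baseline will be assigned to an appropriate analysis visit using the following". Then, if a window holds more than one record, "the record closest to the midpoint of the interval will be used in the analysis". For ties: "If 2 records are tied before and after the middle of the interval, the earlier record will be used in the analysis". None of these rules looks at the value itself.

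Protocol 13.5.1 produces several records close together when the liver is in question: "Any possible hepatic abnormalities will be monitored with repeat testing at a frequency of at least every 72 hours". The frequency falls to weekly or less once the abnormality stabilises.

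SAP 13.5 makes an exception for safety parameters: "all post-baseline assessments will be used for Potentially Clinically Significant (PCS) value determination and all assessments will be presented in the data listings". The PCS laboratory criteria are in SAP Table 1. For the liver they include ALT and AST at >1.5x and >3.0x ULN, and ALT or AST >3x ULN with concurrent total bilirubin >2.0x ULN.

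**The concern.** Retests are ordered because an abnormality has appeared, so a subject's worst value may well fall on one of them. The liver table then takes a single record from the window, chosen by its position in time. A subject whose ALT passed 5x or 8x ULN on a retest can be shown only at the level of the scheduled sample.

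The gap matters most where nothing else in the SAP counts the threshold: ≥5x, >8x, and ≥3x with INR >1.5. A by-visit layout also cannot show how many subjects ever met a criterion, because one subject may appear at several visits or at none. SAP 12 plans no safety monitoring committee for Part B, which puts more weight on the final tables.

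**Working it through.** The plan gives no figure on this point, so there is none to reproduce. The check applies the SAP 13.4 rule to the SAP 13.4.3 windows.

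**Inputs**
- Windows and target days: SAP 13.4.3. There are 22 post-baseline windows: 11 in Part A, 4 in Part B for subjects who transitioned in Part A, and 7 in Part B for subjects who transitioned in Part B.
- Selection rule: closest to the window midpoint, earlier record if tied (SAP 13.4).
- Retest spacing: 3 days, from the 72-hour rule in Protocol 13.5.1.
- Assumption: the scheduled sample falls on its target day and triggers retests at +3, +6, +9 and +12 days.
- The SAP does not define the midpoint of a half-open window, so two conventions were used: (lower + upper)/2 and (lower + upper − 1)/2.

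**Which record is kept**
- Part A: the scheduled record is kept in 9 of 11 windows. The exceptions are Week 4 (21 to <42, midpoint 31.5 or 31, Day 31 kept) and Week 24 (154 to <189, midpoint 171.5 or 171, Day 171 kept).
- Part B, transition in Part A: the scheduled record is kept in 4 of 4 windows.
- Part B, transition in Part B: the scheduled record is kept in 4 or 5 of 7 windows. A retest is kept at T3 (21 to <56, Day 37) and Week 12 (56 to <126, Day 90). T2 (11 to <21) depends on the convention. With midpoint 16, Day 17 is closer than Day 14 (1 against 2 days). With midpoint 15.5, both are 1.5 days away and the earlier, Day 14, is kept.

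Total: 9 + 4 + 4 = 17, or 9 + 4 + 5 = 18, of 22 windows keep the scheduled record and drop every retest in that window. A retest is kept in the other 5 or 4. In four short or late windows (Part A Weeks 2 and 48, T1 and T2) some of the four retests fall after the window closes. The count covers only retests inside the window.

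**Worked example (hypothetical ALT values)**

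Day 168 = 3.5x ULN, Day 171 = 9x, Day 174 = 6x, Day 177 = 4x.
- Part B Week 24 window, 126 to <210: midpoint (126 + 210)/2 = 168. The distances are 0, 3, 6 and 9 days, so Day 168 is kept. The subject counts under ≥3x only. By worst value, the same subject counts under ≥3x, ≥5x and >8x.
- Part A Week 24 window, 154 to <189: midpoint 171.5. Day 168 is 3.5 days away and Day 171 is 0.5, so Day 171 is kept and the 9x peak is tabulated.

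The same episode is therefore reported differently according to where the window's midpoint lies.

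**What the PCS rule recovers**

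| Liver criterion in SAP 7.2 | Matching row in Table 1, using all samples |
|---|---|
| ≥3x | Yes, as >3.0x |
| ≥3x with bilirubin >2x | Yes, as >3x with bilirubin >2.0x |
| ≥3x with INR >1.5 | No |
| ≥5x | No |
| >8x | No |

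SAP 7.2 also specifies no summary table of laboratory PCS values. Its shift table does take unscheduled results, but classes them only as low, normal or high, so 1.1x and 9x ULN fall in the same cell.

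**Size**
- Widest window: Part B Week 12 for subjects who transitioned in Part A, 2 to <126. The SAP prints an interval of 125 days; 126 − 2 gives 124.
- One subject among at most 12 planned per disease is 1/12 = 8.3 percentage points, and more among the subset who enter Part B.

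**The case against.** The strongest reply is that one table is incomplete but the information is not lost. All laboratory values are listed, out-of-range results are flagged and listed separately, and the groups are small enough to check subject by subject. Protocol 15.1.1 has laboratory changes that lead to discontinuation reported as an AE, or as the linked diagnosis. SAP 7.1 tabulates TEAEs leading to discontinuation or dose interruption by system organ class and preferred term, with no one-record-per-window limit. The study is descriptive, so no inference is affected. All of this stands. It does not supply a count of subjects by liver threshold, because preferred terms do not carry the ULN multiple.

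A reader might infer more than the documents support, in four ways:
- That a retest peak always drops out. It does not: SAP 13.4 windows all post-baseline records, and a retest is kept when it is nearest the midpoint.
- That a case with ALT >3x and bilirubin >2x would go unidentified. SAP 13.5 with Table 1 still picks it up from any post-baseline sample.
- That subjects held or stopped under Protocol 13.5.1 cannot be traced. The listings and the TEAE tables allow it, with manual work.
- That the differing signs (≥3x and ≥5x in SAP 7.2, >3x and >5x in Protocol 13.5.1) cause missed cases. The SAP signs are the more inclusive, so no case meeting the protocol's transaminase cut-offs is lost that way.

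**Conclusion.** The point holds as a reporting gap. Followed as written, the SAP can leave a subject who reached ≥5x, >8x, or ≥3x with INR >1.5 on a retest out of the corresponding liver row, and no other specified summary counts subjects at those levels. Under the stated timing assumption the scheduled record displaces the retests in its window in 17 to 18 of 22 windows. That is a count of windows, not a probability of missing a case: the documents give no basis for how often transaminases will rise or on which sample they will peak. A visit off its target day, or retesting that starts at another time, would change which record is kept. The matter concerns tabulation only and leaves the treatment rules in Protocol 13.5.1 untouched.

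**What to change.** Add to SAP 7.2: for each liver criterion, present the number and percentage of subjects meeting it at any time post-baseline, based on the worst value over all scheduled and unscheduled results in the database, by disease group, for Part B and for Part A + B. Keep the by-visit table as secondary.

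The cost is one extra row block per table, built from results already in the database. Reported counts may rise. The wording is limited to results in the database because Protocol 13.5.1 does not say where retests are analysed, so any result held only at a local laboratory would still be missing.

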7.3. Vital Signs

Observed and change from baseline of vital signs (including systolic and diastolic blood pressure, pulse rate, respiratory rate, temperature and body weight) will be summarized at each analysis visit by disease group. All summary tables will be presented for Part B and Part A + B.

Values and changes from Part A + B and Part B baseline values will be listed by disease group. In the listing, values of potential clinical importance will be flagged. These are defined in Table 2:

VS parameter	Criteria
HR	≥100 BPM
	<40 BPM
SBP	≥130 mm Hg
	> 160 mm Hg
	≥ 180 mm Hg
	20 mm Hg increase from baseline
	<90 mm Hg
	\geq 20 mm Hg decrease from baseline
DBP	≥90 mm Hg
	\geq 15 mm Hg increase from baseline
	<40 mm Hg post-baseline or
	\geq 15 mm Hg decrease from baseline
Temp	≥38°C

 Table 2:
 Criteria for Potentially Clinically Significant Vital Signs

7.4. Electrocardiogram (ECG)

For triplicate ECGs, the average value will be used.

Observed and changes from baseline for ECG variables (including heart rate (hr), PR interval, QRS interval, QT interval, QTcB and QTcF interval) will be summarized by analysis visit. QTc interval will be calculated using both Bazett (QTcB=QT/(RR)1/2) and Fridericia (QTcF=QT/(RR)1/3) corrections; and if RR is not available, it will be replaced with 60/hr in the correction formula.

ECG interpretation will be summarized at each analysis visit by disease group. Abnormality shift of normal, abnormal but not clinically significant and abnormal and clinically significant from baseline at each analysis visit will be presented. All summary tables will be presented for Part B and Part A + B.

Observed and changes from Part A +B baseline and Part B baseline values will be listed by disease group. In this listing, values of potentially clinically significant ECG (scheduled or unscheduled) will be flagged. These are defined in Table 3:

ECG parameter	Criteria
HR	< 40 bpm
	> 100 bpm
PR	> 200 msec
QRS	> 120 msec
QTcF	> 450 msec
	> 480 msec
	> 500 msec
QTcF increase from baseline	> 30 msec
	> 60 msec

 Table 3:
 Criteria for Potentially Clinically Significant ECGs

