### 13.2.2. Week 2 to Week 48 (Visits 5-15)

Subjects will self-administer once daily SC doses 360 mg of pegcetacoplan and will attend the investigator site at Visits 5-15 where the assessments outlined in the schedule of events (Section 4), will be performed.

Visit window:  $\pm 2$  days.

Research nurses or other appropriately qualified research personnel will administer the SC infusions until the subject has been qualified to conduct self-administration. Following self-administration qualification, subjects may self-administer the SC infusions. The subject will continue to self-administer infusions at the clinic on those days when a clinic visit occurs and at an off-site location convenient to the subject on all other days. Subjects have the opportunity to transition to a biweekly 1080 mg SC infusion of pegcetacoplan, as early as Week 24 of Part A of the study. If this occurs, the subject will need to have 3 transition visits (T1, T2, and T3), the details of which are provided in Table A1 of Appendix 1.

The following assessments will be performed prior to investigational product administration:

- Procure 3 previously collected consecutive uPCR samples (except Visit 15)
  - Arrange courier pickup for all biweekly triplicate uPCR samples during non-clinic visit weeks
- Dispense 24-hour urine container at Visit 14 (for urine collection within 2 weeks prior to Visit 15)
- Vital sign measurements (to be performed prior to ECG and venipuncture)

- Triplicate 12-lead ECG 15 minutes predose
  - Visit 15: Triplicate 12-lead ECG at -45, -30, and -15 minutes predose
- PK sample predose (within 1 hour before dosing) to coincide with the 15 min predose ECG
- Concomitant medications review
- AE collection and review
- Urinalysis collection (See schedule of events for details)
- eGFR assessment
- Pregnancy (β-HCG) (Visit 15 only), if applicable
- Blood tests (see schedule of events for details)
- Urine pregnancy test, if applicable
- Physical examination (Full exam at Visit 15 only)
- Vaccination Titer Serum Sample (Visit 7 only)
- Vaccination(s) Booster (Visit 7 only)
- Dispense investigational product and infusion materials
- Observe Infusion of investigational product

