### 16.2.3.3. Vital Signs and ECGs

Changes from baseline in vital signs and ECG parameters will be summarized using descriptive statistics by treatment, visit, and nominal time post dose. Baseline will be taken as the last measurement prior to the first dose of pegcetacoplan.

Values of potential clinical significance (eg, increase in QTcF  $\geq$ 30 ms from baseline) will be flagged in listings and summarized by treatment.

ECG parameters will be analyzed using concentration effect models.

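### SAP 2.0 delivers the vital-sign and ECG analyses of Protocol 16.2.3.3 only in part, while SAP 15.1 declares no change

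*SAP*

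**What the plan says.** Protocol 16.2.3.3 sets three analyses.

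- Changes: "Changes from baseline in vital signs and ECG parameters will be summarized using descriptive statistics by treatment, visit, and nominal time post dose".
- Values of potential clinical significance, with a QTcF increase of at least 30 ms as the example: these "will be flagged in listings and summarized by treatment".
- Modelling: "ECG parameters will be analyzed using concentration effect models".

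SAP 7.3 says that observed values and changes in vital signs "will be summarized at each analysis visit by disease group. All summary tables will be presented for Part B and Part A + B". For notable vital signs it says "In the listing, values of potential clinical importance will be flagged", with criteria in Table 2. SAP 7.4 summarises ECG variables by analysis visit, adds a summary and shift table of the ECG interpretation, and treats notable values as follows: "In this listing, values of potentially clinically significant ECG (scheduled or unscheduled) will be flagged", with criteria in Table 3. Neither section mentions time after dosing, a table of notable values or an exposure model for ECG. The entry under SAP 15.1, for changes from the protocol's analyses, is that the section does not apply.

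**The concern.** Protocol 8.3 says that experience to date cannot exclude an unanticipated cardiac risk and that this risk will be evaluated in the study. Change in ECG parameters is a named safety endpoint in Protocol 9.2.6 and SAP 2.1.4. The protocol also schedules the data for the three analyses: vital signs before and after clinic doses, and PK samples taken alongside the ECG.

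If SAP 2.0 is followed as written:

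- an acute effect of the infusion on blood pressure, heart rate or temperature has no summary in which it would show;
- a reader must count affected subjects by hand from the listings;
- the relation between concentration and QTcF is not examined;
- the empty 15.1 entry does not tell the reader that protocol-specified safety analyses were left out.

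**Working it through.** No figure in the plan is at stake, so the check is a comparison of text.

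**Step 1. Does 16.2.3.3 apply to Part B?** Protocol Appendix 1, Section A1.1, says that whatever the appendix does not describe is the same as in the main protocol. The appendix gives no separate analysis methods for vital signs or ECG, so 16.2.3.3 carries over. SAP 1 and 7.3 also extend SAP 2.0 to Part A + B displays for roll-over subjects, and SAP 13.4.3 maps Visits 4 to 15.

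**Step 2. Element by element.**

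| Protocol 16.2.3.3 | SAP 2.0 | Status |
|---|---|---|
| Change "by treatment, visit, and nominal time post dose" | By analysis visit (7.3, 7.4); no time after dosing | In part |
| Notable values flagged and summarised | Flagged in listings (7.3 Table 2, 7.4 Table 3); no table | In part |
| ECG concentration-effect models | None. The modelling text after 8.2 is optional, covers PK and complement markers, and does not name ECG | Absent |

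Count: 0 in full + 2 in part + 1 absent = 3.

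**Step 3. Which post-dose data exist?** Protocol 14.1.5 has vital signs before and 30 minutes after dosing, with further readings at 2 and 4 hours at Visits 4 and 15. The footnotes to Table A1 have them before dosing and within 30 minutes afterwards on Part B clinic dosing days. Scheduled treatment-visit ECGs are all predose (footnotes to Protocol Table 1 and Table A1), so the time-after-dosing element concerns vital signs only.

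**Step 4. What does the windowing rule do with them?** SAP 13.4 keeps one record per window, the one nearest the middle of the interval. If two records tie, one before and one after the middle, the earlier is used. Take the Part B Week 12 window in 13.4.3 (transition in Part B), Day 56 to before Day 126, and a visit on the target Day 84:

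- middle = (56 + 126)/2 = 91;
- predose distance = |84 - 91| = 7 days;
- post-dose distance = |84 - 91| = 7 days.

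The two records tie but lie on the same side of the middle, so the tie rule does not cover them. Taking the middle over whole days 56 to 125 gives 90.5 and a distance of 6.5 days for both, which is the same tie. If the preference for the earlier record is extended to this case, the predose value is kept and the post-dose value leaves the summary. If it is not extended, the choice is undefined. Read literally, at most one of two readings on a Part B clinic dosing day enters the by-visit summary, and at most one of four (predose, 30 minutes, 2 hours, 4 hours) at Visits 4 and 15. Under neither reading is there a separate post-dose summary.

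**Step 5. Are all notable values used?** SAP 13.5 uses every post-baseline assessment to determine notable values and lists every assessment. The information is therefore complete, but no vital-sign or ECG table reports it. By contrast, SAP 7.2 does tabulate liver abnormalities by visit.

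**Step 6. Could the model be fitted?** In Part A the protocol schedules the "PK sample predose (within 1 hour before dosing) to coincide with the 15 min predose ECG". In Table A1, ECG and PK fall together at Week 48 and at the later extension visits, with PK predose or following the ECG. Paired data are therefore collected.

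**The case against.** The strongest reply is about scope and about what the SAP does plan.

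- **Scope.** SAP 2.0 is written for Part B. Part A was analysed under SAP Version 1.0, which is not among the documents. The concentration-effect model and post-dose summaries may have been done there. This stands as a limit: nothing can be said about the Part A analysis. It does not remove the gap in SAP 2.0, because Appendix 1 carries the methods over and the Part A + B displays bring roll-over subjects' Part A records into scope.
- **The cardiac evaluation is there.** A reader might infer that it is not performed, or that none of the three elements is delivered. The documents do not support either. SAP 7.4 plans observed values and changes for heart rate, PR, QRS, QT, QTcB and QTcF, an interpretation summary, a shift table, and flags for QTcF above 450, 480 and 500 msec and increases above 30 and 60 msec.
- **Outliers are visible.** SAP 13.1 reports minimum and maximum, so an extreme value in the analysed record shows in that visit's table. This stands. It does not count affected subjects across visits or include readings that were not the windowed record.
- **Post-dose readings are not lost.** A reader might infer that every one is dropped or blended with predose values. They are listed and used to determine notable values, and blending is only one possible outcome of an unsettled tie.
- **Conditional wording.** The protocol synopsis makes the time-after-dosing breakdown conditional on its being appropriate. This disposes of the point for ECG. It does not for vital signs, where post-dose readings are scheduled.
- **Documentation only.** SAP 15.2 explains that the protocol set no Part B objectives or endpoints, and Protocol 16.2 leaves details to the SAP and sends deviations to the final report. But 15.2 speaks of endpoints and does not mention dropping these safety methods.
- **Small differences.** The QTcF increase of at least 30 ms against more than 30 msec is trivial, since the protocol gives its figure as an example. Summarising by disease group in place of treatment matters little in a single-treatment study.

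**Conclusion.** The point holds as a gap between protocol and SAP in safety reporting. SAP 2.0 has no predose and post-dose breakdown of vital signs, no summary table of notable vital-sign and ECG values, and no ECG concentration-effect model, and SAP 15.1 declares none of this. The size is a count, not a bias or a loss of power: of three specified elements, none is delivered in full, two are in part and one is absent. The effect is on how readily a safety signal would be seen, because the underlying records are collected and listed.

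The conclusion rests on two readings: that Appendix 1 carries 16.2.3.3 into Part B, and that SAP 13.4 is applied to vital signs as written. It makes no claim about the Part A analysis under SAP 1.0. It is worth correcting before the Part B and Part A + B outputs are produced.

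**What to change.** - **SAP 7.3:** summarise predose and each scheduled post-dose nominal time separately within each analysis visit. In 13.4, apply the one-record rule within nominal time so that same-day readings no longer compete.
- **SAP 7.3 and 7.4:** add tables of the number and percent of subjects with any post-baseline value meeting the SAP's own Table 2 and Table 3 criteria, over all scheduled and unscheduled records, for Part B and Part A + B, in the disease groups that Section 7 already uses.
- **SAP 7.4:** add the concentration-QTcF analysis on the paired predose PK and ECG data, or record its removal with a reason in 15.1.
- **SAP 15.1:** replace the present entry with any departure from Protocol 16.2.3.3 that remains.

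The cost is a few more tables and one model. No new data are needed, and no visit or procedure changes.
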